**Effects of Connectivity-based rTMS and State-Dependency
on Amygdala Activation**

NCT03746405

Study Protocol

Date of Approval: February 14th, 2019

This blinded, sham-controlled trial will feature a between-subject design with active or sham rTMS applied over the medial prefrontal cortex, while subjects will be viewing fearful video-clips to engage the stimulated network. Study experimental design is illustrated in **Figure 1A**. Twenty five healthy subjects (18 - 35 years old) will participate. In the initial session, which will last about 2 hours, participants will be consented and screened for eligibility. Resting motor threshold (rMT), defined as the TMS pulse intensity producing on average a 50 μ V peak-to-peak amplitude motor evoked potential, will be assessed using a maximum likelihood method. A 1-hour MRI session that includes a T1-weighted anatomical image and BOLD signal acquisition during passive viewing of fearful and neutral faces in an event-related design, will be performed. Psychophysiological interaction (PPI) or diffusions weighted analyses will be conducted by selecting a seed in the amygdala and defining the spot within the mPFC with the strongest task-related correlation with amygdala activation, or the strongest structural connection with amygdala (**Figure 1B**).

[figure not shown]

Figure 1: A) Illustration of the experiment design. B) Illustration of the psychophysiological interaction (PPI) analysis using the right amygdala as the seed to define a TMS target in the medial prefrontal cortex.

During the second visit, participants will receive active or sham rTMS, counterbalanced across sessions between subjects. 5Hz rTMS will be applied over the mPFC at an intensity up to 120% rMT, replicating parameters used in a promising recent PTSD study. The optimal coil placement during stimulation will be controlled by a neuronavigation system. An electrical sham coil that produces the same auditory and somatosensory stimulations, without a significant magnetic field, will be used as an active control. Participants will view fearful video-clips during rTMS to engage amygdala activation, which we hypothesize will lead to a stronger rTMS effect. Heart rate variability and skin galvanic response will be acquired with the BioPack system during rTMS and will be analyzed as moderators of rTMS efficacy.

To evaluate rTMS-induced changes, MRI will be acquired before and after rTMS, with the acquisition of anatomical scans, resting-state, and task-related functional connectivity, as well as diffusion tensor imaging. These acquisitions will be used to evaluate target engagement within the amygdala and its connectivity with the prefrontal cortex.

Subject Screening:

Twenty-five healthy subjects (18 - 35 years old) will be recruited from the community (to get 19 completers). At the beginning of their first visit to BIAC, they will be screened for the study with a physical examination, the MINI, a handedness questionnaire, and a urine test. If they pass the screening procedure, they will have a short session of TMS (about 0.5 hour), in order to acclimate them to TMS and to obtain right or left hand resting motor thresholds for future dosing of rTMS.

Resting Motor Threshold Determination:

All procedures will occur in Duke Brain Imaging and Analysis Center (BIAC). Resting motor threshold (rMT) is defined as the TMS pulse intensity producing on average a 50 μ V peak-to-peak amplitude motor evoked potential, will be assessed using a maximum likelihood method. rMT is the standard in the field for determining the intensity of rTMS for each individual to reduce seizure risk. The motor evoked potentials (MEP) for the contralateral first dorsal interosseus (FDI) will be measured with EMG. The scalp region producing the largest amplitude MEP will be identified. At that scalp location, the lowest TMS intensity able to elicit 5 MEP's of $\geq 50\mu$ V in peak-to-peak amplitude will be determined, using a using a maximum likelihood estimator (TMS Motor Threshold Assessment Tool, MTAT 2.0, <http://www.clinicalresearcher.org/software.html>). rMT will be determined for one or both hemispheres with the muscle at rest (verified by baseline EMG). Individual MT will be used to determine the intensity of stimulation for each individual, as recommended by safety guidelines.

MRI/fMRI Procedure: Localizer:

At BIAC, after obtaining a T1-weighted anatomical image, fMRI data will be acquired during passive viewing of fearful and neutral faces in an event-related design. Stimuli will be back-projected onto a screen located at the head of the MRI bed using an LCD projector. Subjects will view the screen via a mirror system located in the head coil. Task onset will be electronically synchronized with the MRI acquisition computer. Task administration will be computer controlled. The scanning session will take about 1 hr.

Application of rTMS During Fearful video-clips viewing

rTMS will be applied out of the scanner. Subjects will be seated comfortably in a chair, facing a computer screen positioned in front of the subject for visual stimulus presentation. Earplugs will be worn to protect hearing. The participant's head will be held steady by a frame with a chin rest and the rTMS coil holder frame. A figure-of-eight magnetic coil will be placed on the scalp and held in place with a coil fixing system supplied by MagVenture. This will be paired with a neuronavigation system (BrainSight) which provides precise fMRI-guided rTMS coil placement for basic, translational, and clinical applications of rTMS. The neuronavigation system enables to the coil to be placed at precise cortical targets (the spot within the mPFC showing the strongest task-related correlation with amygdala activation, obtained from the first visit) on the individual's 3-dimensionally rendered brain MRI with less than one millimeter error, and enables to dynamically move the coil to account for slight head movements.

5Hz rTMS will be applied at an intensity up to 120% rMT, stimulation will be applied during 4 seconds separated by 12 seconds of inter-train interval. Sham rTMS will be administered with a sham coil equipped with shielding to block magnetic field output but retain the auditory and some of the tactile aspects of active stimulation. rTMS administration will be controlled by an external computer and will be

time-locked relative to the presentation of fearful video-clips. Heart rate variability and skin galvanic response acquisition will be acquired with a BioPack system during rTMS application and will be analyzed as moderators of rTMS efficacy.

MRI/fMRI Procedure: Evaluation of rTMS-induced changes:

To evaluate rTMS-induced changes, MRI will be acquired before and after rTMS, with the acquisition of anatomical scans, resting-state, and task-related functional connectivity, as well as diffusion tensor imaging. These acquisitions will be used to evaluate target engagement within the amygdala and its connectivity with the prefrontal cortex.

Side effects monitoring:

Subjects' side-effects will be monitored closely. An rTMS side effect rating scale will be administered at the end of each session. Subjects are instructed during the consent process and during the rTMS sessions about all known side effects. They are further instructed during consenting and additionally at the conclusion of the rTMS session to contact the principal investigator or study physician with any questions or concerns (including those that may arise after the experimental session has ended).

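### The only allocation rule asks for balance, leaves *across sessions* unexplained in a between-subject trial, and does not require random or concealed assignment

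*Protocol*

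**What the plan says.** The protocol's opening paragraph sets the design: "This blinded, sham-controlled trial will feature a between-subject design with active or sham rTMS applied over the medial prefrontal cortex". The paragraph after Figure 1 gives the allocation rule for the second visit: "participants will receive active or sham rTMS, counterbalanced across sessions between subjects". No other sentence in either document says how a participant comes to receive active or sham stimulation.

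The first visit is for screening, motor threshold and the localizer MRI. Under Subject Screening, those who pass also receive TMS at that visit ("they will have a short session of TMS (about 0.5 hour"), to get them used to it and to measure the threshold. Only the second visit is described as delivering the intervention. The plan is to enrol 25 people to obtain 19 completers.

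Under Side effects monitoring the session wording is mixed. One sentence reads "An rTMS side effect rating scale will be administered at the end of each session", another mentions the rTMS sessions in the plural ("Subjects are instructed during the consent process and during the rTMS sessions about all known side effects"), and a third has the singular, "at the conclusion of the rTMS session".

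The SAP plans a repeated-measures ANOVA on group data, with stimulation (active, sham) and time (pre, post) as the effects. It has no period or sequence term and says nothing on assignment. The trial is called blinded, but the text does not say who is blinded.

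**The concern.** Two things need separating.

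The first is what the rule means. Counterbalancing across sessions usually means ordering conditions over several sessions of the same person. Here the design is called between-subject and one stimulation visit is described. If the phrase means only that the two arms are to be balanced over people, the words *across sessions* do no work. The point matters because the number of stimulation sessions per person decides whether active and sham are compared between or within people, and so which error term applies.

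The second is what the rule leaves out, and this is the more serious part because it holds under either meaning. Balance is a property of the finished list. It does not say that the order is unpredictable, or that those who enrol cannot see what comes next. If the next assignment can be foreseen, decisions on whom to enrol, whom to bring back for the second visit and when to schedule that visit can differ by arm. With about 19 completers in total, an active-sham difference could then not be securely attributed to stimulation.

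**Working it through.** **Step 1. Which design does the text support?**

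- For parallel arms: the label between-subject; *active or sham* rather than both; a single described stimulation visit; group data in the SAP; no washout, period or sequence term anywhere.
- For more than one stimulation session each: the words *across sessions* in the allocation sentence, and the plurals under Side effects monitoring.
- The plurals have other explanations. They may count the short first-visit TMS session, or the sessions of all participants together. The same section also uses the singular. They do not establish a second stimulation session.

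The parallel reading is therefore the dominant one, with *across sessions* left over. The protocol says that Figure 1A illustrates the experimental design. It was not available for this review and may settle the number of sessions.

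**Step 2. Is random or concealed allocation stated?** Neither text mentions randomisation, sequence generation, an allocation ratio, stratification or concealment. *Blinded* does not supply these: it concerns who knows the treatment, and the text does not say who that is.

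**Step 3. How predictable an order would the rule allow?** The documents give no allocation method, so there is no stated figure to reproduce. The one input from the protocol is N = 25. The assumptions are mine: the person enrolling knows all past assignments and the block size or sizes in use, guesses the more probable arm, and tosses a coin on ties.

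- Strict alternation. The first assignment is unknown and the other 24 are certain. Expected correct guesses: (24 + 0.5)/25 = 0.98.
- Permuted blocks of 4. The six possible orders have 2, 1, 1, 2, 1 and 1 forced assignments, a mean of 8/6 = 1.333 per block. Six blocks give 6 × 1.333 = 8 certain assignments. Expected correct guesses per block are 1/2 + 2/3 + 2/3 + 1 = 2.833. With the 25th a coin toss, (6 × 2.833 + 0.5)/25 = 17.5/25 = 0.70.
- Permuted blocks of 4 or 6, chosen at random with equal probability (simulation of 4,000 lists; the guesser does not know which size comes next). About 1.5 assignments are certain and 0.68 of guesses are correct.
- A concealed random list with past assignments also withheld: 0.50.

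Alternation meets a requirement of balance as well as any random list does, so the stated rule cannot tell these cases apart. Varying the block size cuts the certain assignments from 8 to about 1.5 but barely changes the share guessed (0.70 to 0.68). Withholding past assignments is what brings guessing down to chance.

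**The case against.** The strongest reply is that the wording is loose, not wrong. The design is called between-subject, and balancing arms over people's single sessions is a possible meaning of the sentence. That largely stands. A reader might infer that the protocol contradicts itself, or that a crossover is hidden in it. The documents do not support that: most of the text is parallel, the plurals have innocent explanations, and Figure 1A may resolve the matter. *Ambiguous* is the right word.

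A second reply is that silence on randomisation does not mean that none was used. That also stands. A reader might infer that assignment was by alternation, or that 98% describes this trial. Neither document mentions alternation, and the figure further assumes someone who knows every earlier assignment. It shows what the rule would tolerate and nothing about what was done.

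A third reply is that screening comes first and MRI is acquired before and after stimulation, so the scope for harm is limited. This stands in part. A pre-stimulation scan allows for baseline differences in the measured outcome. It does not remove other differences that foreseeable enrolment or scheduling could create.

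The sham uses its own coil ("Sham rTMS will be administered with a sham coil equipped with shielding to block magnetic field output"), so whoever sets it up might learn the assignment. That is an inference about operator blinding, a separate matter from concealment before enrolment, and the point here does not rest on it.

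**Conclusion.** The point holds in limited form and should be fixed. The single allocation rule is ambiguous, and it requires balance without requiring randomness or concealment. This is more than a missing detail, because a foreseeable order would satisfy the rule as written, and active versus sham is the trial's main question.

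Confidence is high that the text is silent on random and concealed allocation. It is lower on the intended number of sessions, because Figure 1A was not seen. No size can be put on any bias. The predictability figures, from 24 of 25 assignments certain under alternation down to guessing at chance under a concealed list with past assignments withheld, rest on the assumed method and on what the guesser is assumed to know.

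**What to change.** Reconcile the allocation sentence with the between-subject design and check it against Figure 1A. If the design is parallel, as most of the text indicates, replace *counterbalanced across sessions* with approximately 1:1 random allocation after screening, from a computer-generated list. Conceal the list from those who enrol and schedule, and keep past assignments from them as well. The blocking scheme is the sponsor's choice.

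If two stimulation sessions per person are in fact intended, describe the second, randomise the order with concealment, and analyse stimulation as a within-subject factor with a period term.

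As an optional clarification in either case, the SAP could state whether stimulation is a between- or within-subject factor, and that the stimulation-by-time interaction is the test of the active-sham effect. Under the parallel reading both can largely be inferred.

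The cost is a change of wording, preparing the list, and having someone on the existing team outside enrolment hold it. A small imbalance between arms is possible: with blocks no larger than 6, the allocated arms differ by at most 3 wherever enrolment stops. Under the parallel reading no extra participants or visits are needed.

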**Effects of Connectivity-based rTMS and State-Dependency  
on Amygdala Activation**

NCT03746405

Statistical Plan

Date of Approval: February 14th, 2019

To examine whether active rTMS is more effective than sham rTMS to modulate amygdala activation, a repeated measure analysis of variance (ANOVA) will be performed on group data.

Prior to hypothesis testing, functional data will be preprocessed using FSL to remove noise and artifacts. Images will be normalized to a template, motion-corrected, high-pass filtered, and spatially smoothed (8 mm FWHM). Functional activations while subjects will be viewing fearful and neutral faces will be analyzed using standard procedures in FSL. The effects of stimulation (active vs. sham) and time (pre vs. post) will be compared on task-related functional activations. Activations will be considered significant at  $p < 0.05$  with a minimum cluster extent threshold of 5 contiguous voxels. The same ANOVA will be performed on resting state and diffusion tensor imaging acquisitions. Participants with  $> 3$  mm of movement during the acquisitions, will be excluded from the analyses

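### If the arms are parallel and randomised, the planned stimulation-by-time ANOVA is less precise than adjusting the post-rTMS value for the pre-rTMS value, unless the pre-post correlation is high

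*SAP*

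**What the plan says.** The SAP's aim is to find out "whether active rTMS is more effective than sham rTMS to modulate amygdala activation", and for this "a repeated measure analysis of variance (ANOVA) will be performed on group data". Its second paragraph names the factors: "The effects of stimulation (active vs. sham) and time (pre vs. post) will be compared on task-related functional activations". It does not say which term of the ANOVA decides the hypothesis, and it does not use the pre-rTMS value as a covariate. It also excludes participants with more than 3 "mm of movement during the acquisitions, will be excluded from the analyses".

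The Protocol, under the heading on evaluating rTMS-induced changes, says "MRI will be acquired before and after rTMS" and gives the purpose: "These acquisitions will be used to evaluate target engagement within the amygdala". Under Subject Screening, 25 people are recruited "to get 19 completers".

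On design, the Protocol's opening paragraph says the trial "will feature a between-subject design with active or sham rTMS". Its description of the second visit then says the conditions are counterbalanced over sessions. Neither document describes random allocation.

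**The concern.** With two time points, the stimulation-by-time F test is the square of the two-sample t test on post-minus-pre change. A change score fixes the weight on the pre-rTMS value at 1. When the two scans are only moderately correlated, that weight is too large and the noise of the first scan is carried into the comparison. Regression on the pre-rTMS value estimates the weight from the data, at the price of one degree of freedom.

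Precision matters here because the target is only 19 completers, and the motion rule may remove some of them. The pre-rTMS scan is already collected, so precision lost through the choice of analysis could be recovered without extra participants or scans.

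**Working it through.** **Inputs from the documents.** 25 recruited for 19 completers (an implied loss of 1 − 19/25 = 24%); one scan before and one after rTMS; significance level 0.05. The documents give no power, effect size, SD or pre-post correlation, so there is no planned power figure to reproduce.

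**Assumptions.** Parallel randomised arms of 10 and 9; one amygdala value per person; equal pre and post SDs, set to 1; true effect 1 SD; two-sided test; correlation ρ varied.

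**Variances of the estimated active-versus-sham difference.** Let k = 1/10 + 1/9 = 0.2111.
- Interaction (change score): 2(1 − ρ)k, 17 df.
- Adjusted: (1 − ρ²)k × [1 + 1/(N − 4)], 16 df. The bracket is the average cost of estimating the slope; at N = 19 it is 16/15.
- Ratio, adjusted to change score: [(1 + ρ)/2] × 16/15.

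At ρ = 0.5 the interaction variance is 1 × 0.2111 = 0.2111. The adjusted variance is 0.75 × 0.2111 × 16/15 = 0.1689, so the ratio is 0.80. The ratio reaches 1 when (1 + ρ)/2 = 15/16, that is ρ = 0.875.

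**Power.** The interaction uses the noncentral t distribution with 17 df. The adjusted analysis uses 16 df with variance (1 − ρ²)k(1 + T²/17), averaged over the chance baseline imbalance T, which follows a t distribution with 17 df.

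| ρ | Variance ratio | Power, interaction | Power, adjusted | Mean 95% CI half-width, interaction vs adjusted (SD) | N the interaction needs to match adjusted at 19 |
|---|---|---|---|---|---|
| 0.2 | 0.64 | 37% | 53% | 1.21 vs 0.97 | 29 |
| 0.5 | 0.80 | 54% | 63% | 0.96 vs 0.86 | 24 |
| 0.7 | 0.91 | 75% | 79% | 0.74 vs 0.71 | 21 |
| 0.8 | 0.96 | 90% | 91% | 0.60 vs 0.59 | 20 |

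At ρ = 0.9 the ratio is 1.01 and simulated power is 99.6% against 99.4%. Simulation of 100,000 trials per setting gave adjusted power of 52.4%, 63.0%, 79.1% and 90.9% for the four rows, with type I error of 4.9–5.0% for both tests. Power crosses slightly before variance does, at ρ of about 0.85 for a 1 SD effect (0.86 for 0.8 SD, 0.83 for 1.2 SD).

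**Smaller effect (0.8 SD).** 38% against 45% at ρ = 0.5; 74% against 75% at 0.8.

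**Fewer analysed (8 and 8, 1 SD effect).** 31% against 45% at ρ = 0.2; 46% against 54% at 0.5; 84% against 84% at 0.8. The bracket becomes 13/12, so variance breaks even at 2 × 12/13 − 1 = 0.846.

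**Unequal SDs (10 and 9, effect of one pre-scan SD).** If the post SD is 25% larger: 43% against 45% at ρ = 0.5, but 62% against 60% at 0.7 and 78% against 75% at 0.8, where the interaction is ahead. If the post SD is 20% smaller: 61.0% against 81.5% at ρ = 0.5.

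**Largest possible loss.** The change-score variance minus the residual variance after regression is (SD_pre − ρ × SD_post)², which is never negative. The only loss is therefore the slope cost, whatever the correlation or SD ratio: at most 1/15 = 6.7% at 19, or 1/12 = 8.3% at 16.

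**If allocation is not random.** Suppose the arms differ by a stable 0.3 SD and rTMS has no effect. The adjusted estimate is then biased by 0.3(1 − ρ): 0.24, 0.15 and 0.06 SD at ρ = 0.2, 0.5 and 0.8, with false positives of 7.7%, 6.4% and 5.4%. The interaction stays at 5%.

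**The case against.** The planned test is legitimate: under random allocation it holds its error rate, so this is a point about efficiency and not an invalid step. That is right.

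The stronger objection is that the conditions for adjustment are not established. Random allocation is not stated, the counterbalancing phrase allows a crossover reading, and the Protocol's side-effects section speaks of sessions in the plural, although it also uses the singular. Under a crossover this comparison does not apply as stated. Under systematic allocation the change score can be the safer choice, as the bias figures show. This stands, and it is why the recommendation is conditional.

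The calculations also assume one value per person, whereas the SAP describes a voxel-wise test with a cluster-extent threshold; the power figures do not describe that test. Taking the interaction as the deciding term is an inference from the aim and the two factors. Finally, the gain depends on an unknown correlation: it is about one power point at 0.8, and it reverses at 0.9 or if the post-scan SD is sufficiently larger. All of this limits the size of the claim. None of it removes the asymmetry between a possibly substantial gain and a small, bounded loss.

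**Conclusion.** The concern holds as a conditional point about precision. For parallel randomised arms with 19 analysed and equal SDs, baseline adjustment has the lower variance at every correlation below about 0.875. The reduction is 36% at 0.2, 20% at 0.5, 9% at 0.7 and 4% at 0.8. At 0.5 the interaction would need 24 participants, five more than the 19 planned, to match the adjusted analysis. The gain is worthwhile at low to moderate correlation and negligible at high correlation. The documents give no correlation from which to judge where this trial lies. Confidence is medium, because both the design and the correlation are unsettled.

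**What to change.** 1. Reconcile the between-subject description with the counterbalancing over sessions, and state whether allocation to active or sham is random.
2. If the arms are parallel and randomised, define one summary amygdala activation value in advance. Make the efficacy test the active-versus-sham difference in that value after rTMS, adjusted for its pre-rTMS value, with a 95% CI. The voxel-wise maps can stay as planned alongside it.
3. If the ANOVA remains the deciding test, state that the stimulation-by-time interaction alone decides the hypothesis.
4. If participants receive both conditions, or allocation is not random, do not adopt step 2 as written.

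The cost is one degree of freedom, the definition of a summary value the SAP does not now have, and slightly lower precision if the correlation is very high or the post-scan SD is larger than the pre-scan SD, within the limit shown above. No new data are required.

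### The SAP's only significance rule names no multiplicity correction and no search volume; read as an uncorrected voxel-wise threshold, it exceeds a 5% error rate in almost every setting

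*SAP*

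**What the plan says.** The first paragraph of the Statistical Plan sets the question, "whether active rTMS is more effective than sham rTMS to modulate amygdala activation", and assigns it to a repeated-measures ANOVA. The second paragraph smooths the functional images with an 8 mm FWHM kernel and says that responses to fearful and neutral faces "will be analyzed using standard procedures in FSL". Stimulation (active, sham) and time (pre, post) are the factors. The one decision rule is p < 0.05 "with a minimum cluster extent threshold of 5 contiguous voxels". The plan then adds: "The same ANOVA will be performed on resting state and diffusion tensor imaging acquisitions". No separate rule is given for those data.

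In the Protocol, the section on evaluating rTMS-induced changes says the scans serve to "evaluate target engagement within the amygdala and its connectivity with the prefrontal cortex". The Figure 1 legend mentions "using the right amygdala as the seed to define a TMS target", which concerns coil targeting and not the outcome. Subject Screening recruits 25 people "to get 19 completers".

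Neither document states the type or level of the p-value, a correction method, a mask or side for the test, the voxel size, the definition of contiguity, whether tests are one- or two-sided, or the allocation ratio. Neither claims a family-wise error rate.

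**The concern.** A statistical map tests thousands of correlated voxels, so p < 0.05 at each voxel says little about the chance of a false finding somewhere in the volume searched. A minimum cluster size helps only if it is large relative to the smoothness of the noise. Five voxels is small against an 8 mm kernel unless the voxels are large and the search region is tiny.

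The reference to standard FSL procedures does not settle the matter, because it names no correction. Correction, search volume and side could therefore all be chosen after the maps have been seen. With about 19 completers, a chance cluster in the amygdala could be reported as target engagement, and clusters elsewhere would be expected even if rTMS does nothing.

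**Working it through.** The documents give no error rate to reproduce, so the check is what the rule delivers under the null if p is uncorrected and voxel-wise.

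**Inputs from the documents:** p < 0.05; at least 5 contiguous voxels; 8 mm FWHM; 19 completers; stimulation-by-time comparison.

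**Assumptions:** 10 vs 9 completers; voxels of 2, 3 or 4 mm; total smoothness 8 mm; brain (ellipsoid) about 1,434 cm³; amygdala 1.2–1.8 cm³ per side, modelled as two independent spheres.

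**Step 1: the test.** With two groups and two times, the stimulation-by-time test equals a two-sample t-test on the pre-to-post change, with df = 10 + 9 − 2 = 17. Each null run generated 19 smoothed Gaussian change maps, computed t at every voxel, thresholded at p < 0.05, and counted clusters of at least 5 voxels separately by sign.

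**Step 2: scale of the extent rule.** Five voxels occupy 5 × 2³ = 40 mm³, 5 × 3³ = 135 mm³ or 5 × 4³ = 320 mm³. A cube of one FWHM is 8³ = 512 mm³. A 1.5 cm³ amygdala holds about 1,500/8 = 188, 1,500/27 = 56 or 1,500/64 = 23 voxels, so the rule demands about 3%, 9% or 21% of the mask.

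**Step 3: whole brain, two-sided.**

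| Voxel | Runs | Maps with a false cluster | Mean false clusters | Extent for 5% family-wise error |
|---|---|---|---|---|
| 3 mm | 120 | 100% | 142.5 | about 160 voxels |
| 4 mm | 200 | 100% | 70.1 | about 65 voxels |

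At 2 mm, with only 12 runs, all 12 maps were positive.

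**Step 4: amygdala only, two-sided** (400–2,000 runs per setting; ranges cover mask volume and face or 26-neighbour contiguity).

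| Voxel | One side | Both sides |
|---|---|---|
| 2 mm | 36.2–48.7% | 59.3–72.8% |
| 3 mm | 14.7–22.8% | 27.1–40.8% |
| 4 mm | 3.6–6.7% | 7.1–13.0% |

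The two-side figures follow closely from 1 − (1 − p)²; for example, 1 − (1 − 0.362)² = 0.593. One-sided testing of both sides gave 49.8–65.8%, 25.1–40.2% and 9.6–16.4%.

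**Step 5: what the extent rule achieves.** For one side at 1.5 cm³, the false-positive rate falls from 71.0% (any voxel) to 42.3% (at least 5 voxels) at 2 mm, from 61.4% to 17.3% at 3 mm, and from 47.6% to 4.5% at 4 mm.

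**Step 6: sensitivity to smoothness.** Separate runs used ellipsoidal 1.5 cm³ masks, 26-neighbour contiguity and a brain of about 1,605 cm³ (1,500 runs per amygdala setting, 60 per whole-brain setting).

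| Quantity (two-sided) | 8 mm | 12 mm |
|---|---|---|
| One amygdala, 2 mm voxels | 46.6% | 35.3% |
| One amygdala, 3 mm voxels | 21.7% | 18.6% |
| One amygdala, 4 mm voxels | 4.7% | 9.1% |
| Whole brain, 3 mm: maps with a false cluster | 60 of 60 | 60 of 60 |
| Whole brain, 3 mm: mean false clusters | 153 | 81 |
| Whole brain, 3 mm: extent for 5% | about 145 | about 371 |

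**Step 7: the alternative.** A two-sided t-test on the bilateral mask mean rejected in about 1,009 of 20,100 null runs: 1,009/20,100 = 5.0%. Testing a one-side mean in the step 6 runs gave 4.1–5.9% per setting.

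**Step 8: three modalities.** Even with each of task, resting-state and diffusion data held at 5%, the chance of at least one false finding would be 1 − 0.95³ = 14.3% if they were independent.

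**The case against.** The SAP never says that p is uncorrected, and it claims no family-wise rate. The certain defect is missing wording; the percentages show what follows under one reading. That is right, and a corrected p could give adequate control. But the reader cannot tell which was meant, and this is the only rule by which the trial will call anything significant.

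The whole-brain figures can also be said to miss the point, since a cluster outside the amygdala does not answer the stated question. That has force, and the amygdala rates matter more for the trial's claim. They run from about 4% to 73% depending on settings the documents omit. One setting is near nominal: one amygdala, 4 mm voxels, 8 mm total smoothness, two-sided. The SAP fixes only the applied kernel, so it cannot rely on that case, and at 12 mm smoothness the same case gives 9.1%. With no search volume named, whole brain is also the default reading.

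The modelling is open to challenge. Independent masks overstate the two-side rates if noise is positively correlated between sides. Taking 8 mm as total smoothness ignores smoothness already in the data. The Protocol describes a between-subject design but also mentions counterbalancing over sessions; a within-subject analysis (df 18) was not simulated. These points move individual percentages but not the conclusion: whole-brain failure was complete in every setting run, and one-side rates at 2–3 mm stayed well above 5%.

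Finally, choosing an amygdala mean as primary and labelling the other modalities exploratory goes beyond curing the omission. Those are recommendations; stating the correction and search volume is the necessary part.

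**Conclusion.** The concern holds. The significance rule is under-specified, and under the uncorrected voxel-wise reading it does not control error: a false cluster is certain for practical purposes in a whole-brain search, where about 65 to 160 voxels would be needed at 4 and 3 mm instead of 5. Within the amygdala the rate is several times nominal at 2–3 mm voxels. It is moderately raised at 4 mm when both sides are searched, and close to 5% only for one side at 4 mm with 8 mm smoothness.

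Confidence is high for the omission and for the whole-brain failure. The exact amygdala rates depend on the assumed voxel size, smoothness, mask and arm split. All rates apply to the smoothed functional maps; they do not extend to the diffusion data, whose smoothing is not stated.

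**What to change.** 1. State whether p < 0.05 is corrected, at voxel or cluster level, by which method and in which search volume.
2. Make the primary analysis the active-versus-sham comparison of pre-to-post change in the mean fearful-minus-neutral estimate within a pre-specified anatomical amygdala mask. Fix the side before any map is seen: either one test at two-sided 0.05 (right only, or the bilateral mean) or two tests, one per side, at 0.025 each. The right-sided seed in Figure 1B illustrates targeting and does not decide this.
3. For whole-brain maps, replace the 5-voxel rule with a named family-wise correction available in FSL, such as cluster-level FWE p < 0.05 with a stringent cluster-forming threshold (for example Z > 3.1) or permutation-based TFCE.
4. Label the resting-state and diffusion analyses secondary or exploratory, each with its own stated correction.

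The cost is SAP wording; the software is already in the plan. Fewer whole-brain voxels will be declared significant, a bilateral mean may dilute a one-sided effect, and a one-sided mask will miss an effect on the other side.
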